1.3 RATIONALE FOR PERFORMING THE TRIAL

This is a two-stage, multicentre, open-label, randomized, active controlled parallel group study comparing the efficacy and safety of Pramipexole SR versus Pramipexole IR administered orally over an 18-week treatment on nocturnal symptoms in L-Dopa⁺ treated patients with advanced Parkinson's disease (PD).

As reported with other chronic disease, non-adherence of drug use (either mistimed doses or missed doses) is common in parkinsonian patients and may be responsible for failure to relieve symptoms or emergence of drug-related side effects [[P04-06261](#)]. Poorer compliance is associated significantly with taking more anti-parkinsonian tablets per day [[P05-13388](#)].

Sustained release formulations of several products for the treatment of Parkinson's disease have been approved for registration. Sustained release formulation of Pramipexole turned out to be beneficial to parkinsonian patients, by improving patients' convenience and compliance to the treatment.

Concentration of SR is higher than IR in the latter night (11 pm - 4 am on second day) if taking Pramipexole SR once daily after dinner and IR 3 times daily which may result in potential benefit on nocturnal symptoms.

The general aim of study stage I is to explore the efficacy of Pramipexole SR versus Pramipexole IR (as measured by the change from baseline to week 18 in Parkinson's disease Sleep Scale-2 (PDSS-2) total score) in treating nocturnal symptoms in patients on L-Dopa⁺ with advanced PD. The general aim of study stage II is to further evaluate or confirm the efficacy between Pramipexole SR versus Pramipexole IR (as measured by the change from baseline to week 18 in PDSS-2 total score) in treating nocturnal symptoms in patients on L-Dopa⁺ with advanced PD based on the results from Stage I.

Patients must be treated with L-Dopa⁺ (i.e. standard and/or sustained release Levodopa/DDC inhibitor), or with a combination of L-Dopa⁺ and entacapone, at an optimized dose according to investigator's judgment, this dose being stable for at least 4 weeks prior to randomization visit. Sustained release Levodopa/DDC inhibitor must not be used after supper within 4 weeks prior to randomization visit.

Pramipexole IR will be administered in equally divided doses 3 times per day and Pramipexole SR will be administered once daily at 7-9pm before bedtime. After a 1- to 2-week screening phase, patients will be randomized to one of the two treatment groups, with a balanced ratio of 1:1 (Pramipexole SR: Pramipexole IR). During the 7-week up-titration phase, the dose of study medication will be up-titrated until the optimal daily dose is reached. The degree of improvement will be based upon the clinical judgement of the investigator. At the end of this up-titration phase, patients will enter the 11-week maintenance phase. The maintenance dose of study medication will be the optimal daily dose reached at the end of the up-titration phase. Following the maintenance-phase, patients will enter a short dose reduction phase which can last for up to 7 days (depending on the daily dose administered during the maintenance-phase) or continue Pramipexole IR/SR treatment judged by investigators and patients with commercial supply at visit 7. The purposes of the dose-reduction phase are to gradually reduce the dose of Pramipexole, to prevent possible Adverse Events associated with rapid dose-reduction.

The primary efficacy endpoint used to evaluate the patient's treatment response will be PDSS-2 total score (change from baseline to the end of the maintenance period). Secondary efficacy endpoints and safety endpoints are described in [Section 2.1](#) and [2.2](#).

1.4 BENEFIT - RISK ASSESSMENT

The efficacy and tolerability of both Pramipexole IR and SR have been demonstrated in both early [[U95-0560](#); [U95-0588](#); [U00-0074](#); [U09-1232-03](#)] and advanced [[U95-3150](#); [U96-0232](#); [U09-1270-04](#)] PD trials. In addition, non-inferiority between Pramipexole SR and Pramipexole IR was demonstrated after 33 weeks of treatment in an international Phase III trial in patients with early PD, at similar mean total daily dose of Pramipexole and similar dose distribution in the two groups [[U09-1232-03](#)].

This study is designed to explore firstly, then further evaluate or confirm the efficacy between Pramipexole SR versus Pramipexole IR (as measure by PDSS-2 score) in Chinese PD patients.

A flexible up-titration design will be used in the trial, to allow each patient to be up-titrated until an optimal therapeutic response is achieved. The dose range for Pramipexole SR (from 0.375 mg to 4.5 mg per day) is identical to daily doses approved for Pramipexole IR [[U04-1242-06](#)] and to the dosing scheme used in previous international and local Phase III trials for the clinical development of Pramipexole SR [[U09-1232-03](#)] and [[U09-1270-04](#)].

Exclusion criteria have been defined in the trial according to the Pramipexole Summary of Products Characteristics (SmPC). At each study visit, adverse events will be elicited by asking the patients how they have felt since the last visit. The study duration and procedures do not expose the patients to any specific risk, as a treatment (Pramipexole SR or IR) will be given to all patients, and this treatment may be taken concomitantly to any other antiparkinsonian treatments (anti-parkinsonian anticholinergics, MAO-B-inhibitors, amantadine, entacapone, L-Dopa⁺). In addition, patients and investigators may decide to discontinue the study at any time.

2. TRIAL OBJECTIVES AND ENDPOINTS

2.1 MAIN OBJECTIVES, PRIMARY AND SECONDARY ENDPOINTS

2.1.1 Main objectives

The main objective of the study is to explore firstly, then further evaluate or confirm the efficacy between Pramipexole SR versus Pramipexole IR on nocturnal symptoms (as measured by the change from baseline to the end of the maintenance period in PDSS-2 score) in L-dopa⁺ treated patients with advanced PD.

2.1.2 Primary endpoint(s)

The primary endpoint is the change from baseline to week 18 in PDSS-2 total score.

2.1.3 Secondary endpoint(s)

Secondary efficacy endpoints are (to be assessed at week 18):

- Nocturnal Hypokinesia Questionnaire (NHQ) score (change from baseline);
- SCOPA-Sleep score (change from baseline);
- Early Morning Off (EMO) score (change from baseline);
- Responder rate for PDSS-2 total score < 18;
- Responder rate for EMO score;
- The Parkinson's disease Questionnaire (PDQ)-8 score (change from baseline);
- Responder rate for Clinical Global Impression of Improvement (CGI-I);
- Responder rate for Patient Global Impression of Improvement (PGI-I);
- Epworth Sleepiness Scale (ESS) score (change from baseline).

3. DESCRIPTION OF DESIGN AND TRIAL POPULATION

3.1 OVERALL TRIAL DESIGN AND PLAN

This is a two-stage, multicentre, open-label, randomized, active controlled parallel group to compare the efficacy and safety of Pramipexole SR versus Pramipexole IR administered orally for 18 weeks in Chinese patients with advanced Parkinson's disease (PD) treated with L-Dopa⁺ (i.e. standard and/or sustained release L-Dopa /DDC inhibitor). After a 2-week screening phase and a 7-week flexible up-titration phase, there will be an 11-week maintenance phase, followed by a 1-week down titration phase. Therefore, the trial can last for up to 21 weeks totally. Investigators in this study will be neurologists. More details about the administrative structure of the trial are given in the Investigator Site File (ISF). During the trial, there will be 8 visits and 5 telephone calls (see [Flow Chart](#)).

The stage I part of this trial will be conducted as a pilot study to explore the difference of change from baseline to week 18 in PDSS-2 total score between Pramipexole SR and IR. Stage II will be planned as a confirmatory or exploratory design. Stage I and II are totally separated, and the patients in Stage I will not be used in Stage II.

3.2 DISCUSSION OF TRIAL DESIGN, INCLUDING THE CHOICE OF CONTROL GROUP(S)

The trial will be conducted using a two-stage, open-label, randomized, active controlled parallel-group design.

The phase IV study was designed as two-stage due to the limited prior clinical evidences and the unclear deviations in the target population. Therefore, the Stage I was designed as a pilot to detect the signal. Based on the favorable results from Stage I, the Stage II will be continued for further confirmation or further evaluation.

There will be two treatment arms in this trial: Pramipexole SR as investigational medication, Pramipexole IR as an active control. Placebo won't be used in this study.

A double-blinded trial requires either over-encapsulation and subsequent equivalency testing be completed for two distinct packaging schema of the comparator (i.e. one Aluminium-aluminium blister in Pramipexole SR and three Aluminium-aluminium blisters-packaging in Pramipexole IR and unbalanced nature of different dose for each tablet between Pramipexole IR and Pramipexole SR). Therefore, this study will be conducted in an open-label fashion. But this study will use randomization to minimize the potential bias incorporated.

3.3 TRANSITION FROM STAGE I TO STAGE II

The guidance described in the [Table 3.3:1](#) serves as decision making rules for transition to Stage II.

Table 3.3:1 Guidance for decision making for transition to Stage II

Scenarios	Result of primary endpoint in Stage I			Decision making for Stage II
	Clinical value		Statistics	
A	Achieve the minimal clinically important difference (MCID): The adjusted mean difference ≤ -3.44	AND	$P < 0.05$	Stop
B	Achieve MCID The adjusted mean difference ≤ -3.44	AND	$P \geq 0.05$	Continue
C	Not achieve MCID The adjusted mean difference > -3.44	AND	Any P	Stop

NOTE: The adjusted mean difference is the primary analyse result of the primary endpoint.

In summary, there are 3 scenarios for decision making for transition to Stage II based on Stage I results as below,

- Scenario A - Stop upon achieving MCID[R17-4026] (i.e., the adjusted mean difference ≤ -3.44 at Stage I) and statistical significance ($P < 0.05$);
- Scenario B - Continue upon achieving MCID (i.e., the adjusted mean difference ≤ -3.44 at Stage I) and no statistical significance ($P \geq 0.05$);
- Scenario C - Stop upon not achieving MCID (i.e., the adjusted mean difference > -3.44 at Stage I).

For Scenario B and C, the analysis results of Stage I in conjunction with other factors will be used to allow BI to make a joint decision on whether the benefit and risk support the continuation of the trial into Stage II. For example, in Scenario C, if there is another endpoint showing great benefit of SR, the trial may continue into Stage II with this endpoint as the primary endpoint.

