7.2 NULL AND ALTERNATIVE HYPOTHESES

For pilot stage I, there is no (confirmatory) hypothesis testing foreseen in a strict statistical sense. Analyses are descriptive in nature including two-sided p-values and confidence intervals throughout from statistical models used for explorative purposes.

For stage II, the assumption of the hypothesis testing will be based on the results of pilot stage I, which will be added once the topline results of stage I are worked out.

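### Does stopping the trial after the most favourable Stage I result contradict the plan to go on and confirm?

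*Protocol*

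**What the plan says.** Section 3.3 sorts the Stage I primary result into three scenarios.

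- **A**, MCID reached and P < 0.05: "Scenario A - Stop upon achieving MCID[R17-4026] (i.e., the adjusted mean difference ≤ -3.44 at Stage I) and statistical significance".
- **B**, MCID reached and P ≥ 0.05: "Continue upon achieving MCID (i.e., the adjusted mean difference ≤ -3.44 at Stage I) and no statistical significance".
- **C**, MCID not reached, whatever the p-value: stop.

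A clause below the table gives the sponsor room for judgement in two of the three: "For Scenario B and C, the analysis results of Stage I in conjunction with other factors will be used". For C it adds an example: "if there is another endpoint showing great benefit of SR, the trial may continue into Stage II with this endpoint as the primary endpoint".

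Section 3.2 explains the two stages. It says that "the Stage I was designed as a pilot to detect the signal", and then: "Based on the favorable results from Stage I, the Stage II will be continued for further confirmation or further evaluation". Section 2.1.1 is similar: "The main objective of the study is to explore firstly, then further evaluate or confirm the efficacy". On the status of Stage I inference, section 7.2 states that "there is no (confirmatory) hypothesis testing foreseen in a strict statistical sense". Section 7.3.1 also labels the p-values as descriptive. Sections 3.1 and 7.1 keep the two stages separate, with no Stage I patient carried into Stage II.

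**The concern.** Read 3.2 alone and a clear success in Stage I should open Stage II. Read 3.3 and the same success closes the trial, under the same word that C uses for failure. The room for judgement covers B and C but not A, so a result that misses the MCID has a route to Stage II and the best result has none. Nothing in 3.3 says that A is a stop for success. The trial would then end on a p-value that 7.2 does not treat as a test.

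If this were a true contradiction, the sponsor could be unsure what to do after Stage I, or could choose between 3.2 and 3.3 once the result was known. It would also matter often, because under the planning assumptions A is the usual way of reaching the MCID.

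**Working it through.** **Inputs.** From section 7.7: SD 8 and 80 evaluable patients, taken as 40 per arm under 1:1 allocation. From section 3.3: cut-off -3.44 and P < 0.05, two-sided as in 7.3.1. The protocol gives no standard error for the model-adjusted week-18 contrast, so the two-sample standard error behind Table 7.7:1 stands in for it.

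**Reproducing the plan's figure.** SE = 8 × √(2/40) = 1.789. The chance that the observed difference is at or below -3.44 is Φ((-3.44 - true)/SE).

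- True -4: Φ(0.56/1.789) = Φ(0.313) = 62.3%.
- True -5: Φ(1.56/1.789) = Φ(0.872) = 80.8%.

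Both agree with section 7.7, and the other cells of the table reproduce as well.

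**Splitting that chance into A and B.** With t(0.975, 78) = 1.991, significance begins at 1.991 × 1.789 = 3.561. At an observed SD of 8, B covers differences from -3.44 to -3.56, a width of 0.12 points. Allowing for sampling variation in the SD, the chances at N = 80 are (rows may miss 100 by rounding):

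| True difference | SD | A | B | C |
|---|---|---|---|---|
| -3.44 | 8 | 46.1% | 3.9% | 50.0% |
| -4 | 8 | 58.4% | 3.8% | 37.7% |
| -5 | 8 | 77.9% | 2.9% | 19.2% |
| -4 | 7 | 63.7% | 0.3% | 36.0% |
| -4 | 9 | 50.0% | 10.9% | 39.0% |
| -4 | 10 | 42.3% | 17.5% | 40.1% |
| -4 | 12 | 31.3% | 27.0% | 41.7% |

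With no true difference and SD 8, A occurs 2.2% of the time.

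**What the figures show.** A is the common route to the MCID if the SD is near 8. The share going to B grows steadily with the SD. Section 3.2 gives uncertainty about variability in this population as one reason for having two stages. B is the branch for the case where the effect looks large enough but the data are noisier than planned. A small B at SD 8 is what such a branch should look like. Nor is P(B) the overall chance of Stage II, because C may continue by joint decision and that cannot be computed.

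**Setting the passages side by side.**

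1. *Is the action determinate?* Yes. Table 3.3:1 and the list beneath it both give stop for A, and the clause on sponsor judgement leaves A out. Amendment 1 corrected the p-value sign in the non-significant scenario of this section and lists no change to the action in A.
2. *Does 3.2 promise Stage II after every good result?* Not necessarily. It leaves favourable undefined and comes directly before the section that sets the rule. B is a favourable result that continues, so the sentence has a natural meaning under 3.3. The synopsis also makes Stage II depend on a decision to continue.
3. *Is the status of a Scenario A result open?* No. Section 7.2 makes Stage I descriptive and exploratory, and 7.7 describes it as a pilot to inform the next decision. A p-value can serve as one part of a go/no-go rule and remain descriptive.
4. *Is any error rate affected?* No. The stages share no patients, so choices made after Stage I do not inflate the Stage II error.

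**The case for a change.** The strongest case for a change is that 3.2 is inaccurate as worded. If A is a success stop, Stage II follows an MCID-sized result that lacks significance, not favourable results in general. A programme would then end on an unconfirmed p-value in an open-label pilot, and explaining what A means only after seeing the data would look result-driven. A few sentences before Stage I data are seen would prevent this.

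The first part stands: taken literally, 3.2 could include A, and 3.3 gives no reason for stopping there. The rest does not lead to a change. The action in A is already fixed in advance, so there is nothing to decide after the fact, and 7.2 already rules out a confirmatory claim. Explanatory sentences would leave every action and analysis as it is.

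Turning A into a continuation would alter the design. At true -4 and SD 8 it would raise the tabulated chance of continuing from about 4% (B) to about 62% (A and B together). Whether a significant, MCID-sized pilot result justifies a second trial is a programme and budget choice, and no error in the sponsor's choice has been shown. Pointing row C to its exception, which stands in the same section, is copy-editing.

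**Conclusion.** No change to the plan is called for. Sections 3.2 and 3.3 are worded loosely against each other, but 3.3 is the operative rule and gives one clear action for each result, subject to the joint decision it reserves for B and C. Following it in Scenario A ends the trial with an exploratory finding, as 7.2 provides. At SD 8 and true -4, about 58% of trials would end in A and about 4% would fall in B. Those figures rest on the planning SD and on a two-sample standard error in place of the adjusted contrast, and B ranges from 0.3% at SD 7 to 27% at SD 12. They describe the rule and do not show it to be wrong. The 62.3% in section 7.7 is correct. The conclusion assumes that A is meant as a stop for a sufficient signal, which is the natural reading of a rule stated twice in the same section.

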3.4 SELECTION OF TRIAL POPULATION

A total of 86 eligible, male and female patients with advanced PD, Modified Hoehn and Yahr stages 2 to 4 at on-time with motor fluctuations and nocturnal symptoms (determined by PDSS-2 total score ≥ 18) will be randomized in stage I.

It is anticipated that approximately 102 patients will be screened and 86 eligible patients will be obtained for randomization in stage I (assuming a 15%-screening failure rate).

The sample size of stage II will be calculated based on the results from stage I.

Approximately 10 to 15 centers will be selected for the trial. Investigators who fail to enter at least one patient in the first three months after trial initiation at each center may be excluded from the further participation. If recruitment is delayed, additional centers can be recruited.

Screening of patients for this trial is competitive, i.e. screening for the trial will be stopped at all sites at the same time once a sufficient number of patients has been screened. Investigators will be notified about the screening completion and will then not be allowed to screen additional patients for this trial.

This clinical study can fulfill its objectives only if appropriate patients are enrolled. The following eligibility criteria are designed to select patients for whom Pramipexole treatment is considered appropriate. All relevant medical and non-medical conditions should be taken into consideration when deciding whether this protocol is suitable for a particular patient. A log of all patients enrolled into the trial (i.e. who have signed the informed consent) will be maintained in the ISF at the investigational site irrespective of whether they have been treated with investigational product or not.

3.4.1 Main diagnosis for trial entry

Please refer to [section 8.3.1](#) (Source Documents) for the documentation requirements pertaining to the in- and exclusion criteria.

3.4.2 Inclusion criteria

1. Male or female patient with advanced idiopathic PD confirmed by at least bradykinesia and one of the following signs: resting tremor, rigidity.
2. Diagnosed as Parkinson's disease, with at least 2 years' PD history.
3. Of age ≥ 30 years at time of diagnosis.
4. Modified Hoehn and Yahr stage of 2 to 4 at on-time.
5. They must have clinically relevant sleep disturbances (i.e. PDSS-2 total score ≥ 18 at baseline).
6. They must feel uncomfortable at night because they were unable to turn around in bed or move due to immobility (i.e. the scoring of question 9 in PDSS-2 ≥ 2 , which means frequency is at least 2 to 3 days during the past week).
7. They must have early morning off (i.e. the frequency of "feeling like bodily movements are poor when you wake up?" is at least 2 to 3 days during the past week).
8. Patients must have motor fluctuations (at least 2 cumulative hours of off-time every day during waking hours, documented on a patient diary completed for 2 consecutive days before randomization visit).
9. Patients must be treated with L-Dopa⁺ (i.e. standard and/or sustained release Levodopa/DDC inhibitor), or with a combination of L-Dopa⁺ and entacapone, at an optimized dose according to investigator's judgment, this dose being stable for at least 4 weeks prior to randomization visit.
10. Patients must not have been treated with sustained release dopaminergic drug (i.e. sustained release Levodopa/DDC inhibitor) after supper, or any anti-PD medication after 9pm within 4 weeks prior to randomization visit.

11. Patients must not have been treated with dopamine agonists within 4 weeks prior to randomization visit. A concomitant treatment with one or more of the following drugs will be allowed (at a stable dose for at least 4 weeks prior to randomization visit and the investigator does not intend to change this treatment during the treatment phase):
 - Anti-parkinsonian anticholinergics;
 - Selegiline, rasagiline, or other MAO-B-Inhibitor;
 - Amantadine;
 - Entacapone (or other COMT-Inhibitor).
12. Male or female patients. Women of childbearing potential (WOCBP)¹ and men able to father a child must be ready and able to use highly effective methods of birth control per ICH M3 (R2) that result in a low failure rate of less than 1% per year when used consistently and correctly. A list of contraception methods meeting these criteria is provided in the patient information.
13. Signed and dated written informed consent in accordance with ICH-GCP and local legislation prior to admission to the trial.

3.4.3 Exclusion criteria

1. Secondary parkinsonian syndromes due to drugs (e.g., metoclopramide, flunarizine), metabolic disorders (e.g., Wilson's disease), encephalitis or degenerative diseases (e.g., progressive supranuclear palsy).
2. Dementia, as defined by a Mini-Mental State Exam score < 24 at screening visit [[R96-2656](#)].
3. Any psychiatric disorder according to DSM-V Diagnostic and Statistical Manual of Mental Disorders, 5th edition criteria that could prevent compliance or completion of the study and/or put the patient at risk if he/she takes part in the study.
4. History of psychosis, except history of drug induced hallucinations (provided the investigator considers that participation to the trial would not represent a significant risk for the patient).
5. History of deep brain stimulation.
6. History of nucleus lesioning.
7. Clinically significant electrocardiogram (ECG) abnormalities at screening visit, according to investigator's judgement.
8. Clinically significant hypotension (i.e. supine systolic blood pressure < 90 mmHg) and/or symptomatic orthostatic hypotension (i.e. clinical symptoms of orthostatic hypotension

¹ A woman is considered of childbearing potential (WOCBP), i.e. fertile, following menarche and until becoming post-menopausal unless permanently sterile.

Permanent sterilisation methods include hysterectomy, bilateral salpingectomy and bilateral oophorectomy.

Tubal ligation is NOT a method of permanent sterilisation.

A postmenopausal state is defined as no menses for 12 months without an alternative medical cause.

associated with a decline ≥ 20 mmHg in systolic blood pressure and a decline ≥ 10 mmHg in diastolic blood pressure, at 1 minute after standing compared with the previous supine systolic and diastolic blood pressure obtained after 5 minutes of quiet rest) at screening or randomization visit.

9. Major surgery (major according to the investigator's assessment) performed within 12 weeks prior to randomization or planned within 12 months after screening, e.g. hip replacement.
10. Any other clinically significant disease, whether treated or not, that could put the patient at risk or could prevent compliance or completion of the study.
11. Serious Sleep Apnea Hypopnea Syndrome (i.e. the scoring of question 15 in PDSS-2 ≥ 3 , that means frequency is at least 4 to 5 days during the past week)
12. Any documented active or suspected malignancy or history of malignancy within 5 years prior to screening, except appropriately treated basal cell carcinoma of the skin or in situ carcinoma of uterine cervix.
13. Serum levels of AST (SGOT), ALT (SGPT), alkaline phosphatases or total bilirubin >2 ULN (on screening lab test).
14. Patients with a creatinine clearance < 50 mL/min (estimated by the local lab / the investigator using the Modification of Diet in Renal Disease (MDRD, please refer to [Appendix 10.1](#)), and calculated on screening lab test).
15. Any hypnotic medication within 4 weeks prior to the randomization visit (i.e. diazepam, clonazepam, estazolam, alprazolam, zolpidem, etc.).
16. Any medication (including intra-muscular formulations) with central dopaminergic antagonist activity within 4 weeks prior to the randomization visit (i.e. typical neuroleptics, atypical antipsychotics, reserpine, methyldopa, centrally-active antiemetics, etc.).
17. Any of the following drugs within 4 weeks prior to randomization visit: methylphenidate, cinnarizine, amphetamines.
18. Flunarizine within 3 months prior to randomization visit.
19. Known hypersensitivity to Pramipexole or its excipients.
20. Patients who must or wish to continue the intake of restricted medications (see [section 4.2.2.1](#)) or any drug considered likely to interfere with the safe conduct of the trial.
21. Previous enrolment in this trial.
22. Currently enrolled in another investigational device or drug trial, or less than 30 days since ending another investigational device or drug trial(s), or receiving other investigational treatment(s).
23. Chronic alcohol or drug abuse or any condition that, in the investigator's opinion, makes them an unreliable trial patient or unlikely to complete the trial.
24. Women who are pregnant, nursing, or who plan to become pregnant in the trial.

